4.2. Study Efficacy Endpoints

4.2.1. Primary Efficacy Endpoint

The primary efficacy endpoint is the event rate of new PEx per subject per 28 weeks using the primary definition of new PEx comparing the lenabasum 20 mg BID and placebo cohorts. The event rate is based on the occurrence of new PEx, and the occurrence will be assessed during the treatment phase. It is defined as follows:

The primary endpoint will be calculated by the following for each treatment cohort:

Event rate of PEx (per subject-28 Weeks) for a treatment group is calculated as follows:

Total number of PEx using primary definition during the treatment period / [sum of subject treatment exposure durations in the treatment group (days) / 196]

[figure not shown]
Event rate of PEx (per subject) for a treatment group (without adjustment of treatment exposure) is calculated as follows:

Total number of PEx using primary definition during the treatment period / number of subjects in the treatment group

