3. STUDY OBJECTIVES

3.1. Primary Efficacy Objective

[figure not shown]
The primary efficacy objective is to evaluate the efficacy of lenabasum compared to placebo in the treatment of cystic fibrosis (CF) by assessing the event rate per subject per 28 weeks of new pulmonary exacerbations (PEx), using the primary definition of new PEx, comparing lenabasum 20 mg twice per day (BID) and placebo cohorts. The assessment for the primary objective occurs during the treatment period, from Day 1 to Visit 8 (Week 28).

[figure not shown]

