4.1.3. Possible Pulmonary Exacerbation Visit

Subjects who experience new or worsening respiratory symptoms or who receive a prescription for a new antibiotic from a physician other than a study physician should contact the site staff and return for a Possible PEx Visit if instructed to do so. If determined that a visit is needed, a Possible PEx Visit should be scheduled as soon as possible. Though it is expected that this visit will be in person at the study sites, there may be occasions that this visit is completed over the telephone by the investigator.

If the visit is completed in person (preferred), the following assessments will be done:

- Subject-reported outcomes preferably obtained from the subject before other visit assessments.
 - CRISS questionnaire
 - CFQ-R questionnaire
- AE monitoring
- Record concomitant medications
- Vital signs and central BMI calculations
- Blood and urine tests
 - CBC with differential cell count and platelets
 - Metabolic panel
 - Urine dipstick
 - CRP, ESR and other inflammatory biomarkers
- Spirometry
- Attempt sputum collection
- Physician assessment of:
 - Brief physical examination
 - Antibiotic Use for Respiratory Signs and Symptoms Questionnaire (AUR-Q)

If the visit is completed over the telephone, the following assessments will be done:

- AE monitoring.
- Record concomitant medications.
- Physician assessment of:
 - AUR-Q

Some subjects may receive antibiotic therapy for new or worsening pulmonary symptoms or systemic symptoms from a physician other than the study investigator. In this case, site staff will ask the subject to return for a Possible PEx Visit as soon as feasible. Though it is expected that this visit will be in person at the study site, there may be occasions that this visit is completed over the telephone by the investigator. The investigator will assess the subject and complete the AUR-Q.

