4.1.12. Discontinuation from Study Product but Continuation in Study

A subject may discontinue study product and continue in the study. If a subject permanently discontinues study product, they will be asked to continue in the study for efficacy and safety follow-up with Visits 5 and 8 performed off study product, starting with the next one of these visits that occurs after discontinuation of study product. For subjects who do not withdraw consent and agree to return for these visits, an additional 28-day safety follow-up after Visit 8 will not be done. Safety and efficacy data will be collected during these visits and included in analyses of safety and efficacy data. The impact of having these subjects remain in the study will be assessed in sensitivity analyses of the primary and first secondary efficacy outcomes.

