5. ASSESSMENT AND DERIVATION OF EFFICACY AND BIOMARKER ENDPOINTS

5.1. Primary Efficacy Endpoint

The primary efficacy endpoint will be based on the occurrence of new PEx. The occurrence of a new PEx will be assessed throughout the active dosing period. The primary comparison of the

lenabasum 20 mg BID treatment cohort to the placebo cohort will be based on the event rate of PEx per subject per 28 weeks using the primary definition of PEx.

The event rate comparison is calculated as follows:

$$\theta = R_l / R_p$$

where R_l is the event rate of PEx per subject per 28 weeks using the primary definition of PEx for the lenabasum treatment cohort, and R_p is the event rate of PEx per subject per 28 weeks using the primary definition of PEx for the placebo group.

See [Section 4.2.1](#) for the calculation of the event rate of PEx per subject per 28 weeks.

At screening and again at Visit 1, subjects and/or their legally acceptable representative will be instructed when and how to call the site staff to report new or worsening respiratory or systemic symptoms. Subjects who experience new or worsening respiratory symptoms or have received a prescription for a new antibiotic from a physician other than a study physician should contact the site staff and return for an unscheduled Possible PEx Visit if directed to do so.

At each visit, the investigator will assess the subject for the presence of any new or worsening respiratory symptoms. The physician will assess medical history for changes from last visit, perform physical examination of the lungs and physical examination of other organs as indicated by change in medical history, and complete the AUR-Q (refer to Case Report Form).

The AUR-Q questionnaire includes Fuchs criteria (Fuchs et al, 1994) and a list of additional signs and symptoms, that may have led a physician to make a diagnosis of pulmonary exacerbation. At least 4 out of 12 Fuchs criteria are required to make a diagnosis of a new PEx by the primary definition, but not by the secondary definition.

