5.1.1. Primary Definition of New Pulmonary Exacerbation

The derivation for new PEx by the primary definition is provided below. The rules for defining new antibiotics used for new PEx, including the start and stop days, are also provided below.

Primary definition of new PEx:

- Physician diagnosis of PEx
- Prescription of new antibiotics for PEx
- Start date of new antibiotics for PEx is > 28 days after the stop date of any antibiotics given for any previous PEx. The physician does not need to determine if there is > 28 days from last use of antibiotics to the new antibiotics for PEx analysis purposes. The > 28-day gap will be determined centrally
- A new PEx is not defined by the number of antibiotics prescribed or the order or route of administration of the antibiotics (oral or IV) for that new PEx
- ≥ 4 out of 12 Fuchs criteria are met

New antibiotics for PEx

- Must be given for PEx

- Must be administered by oral or IV route
- Start date is day the physician prescribes that the subject should take this antibiotic treatment for a PEx
- Stop date is the last day the physician prescribes that the subject should take this antibiotic treatment for a PEx
- Start day > Day 1
- Start day \leq Day of Visit 8 or discontinuation from the study
- Regularly given prophylactic inhaled, oral, or IV antibiotics do not count as new antibiotics unless the dose is increased or given early for a PEx

Start day of a new PEx:

The first day that the physician prescribes that the subject should take any new antibiotic treatment for that new PEx

Stop day of a new PEx:

The last day that the physician prescribes that the subject should take any new antibiotic treatment for that new PEx or day of discontinuation from the study, whichever is sooner

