6.3. Sample Size and Power Considerations

The study is expected to enroll approximately 415 subjects, with ~166 subjects each in the lenabasum 20 mg BID and placebo BID cohorts and ~83 subjects in the lenabasum 5 mg BID cohort (accounting for an approximate 15% dropout rate). The study provides 80% power to detect a significant difference between the lenabasum 20 mg BID dose and placebo in the primary endpoint (PEx event rate) at a two-sided alpha of 0.05. This is based on an event rate ratio of 0.65 (a 35% event rate reduction in the lenabasum group), when the event rate in the control group is 0.80.

This also provides 90% power to detect a significant difference between lenabasum 20 mg BID and placebo BID in the secondary endpoint of time to first PEx. This is based on an estimate of the probability of an event (PEx) in the placebo group of 0.60, an estimated hazard ratio of 0.60 (risk reduction 0.40), and the probability of an event in the lenabasum group of 0.36.

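### Exacerbations are counted to Visit 8 or leaving the study, but the primary rate divides by days to last dose, and time to first exacerbation censors only event-free subjects at last dose

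*SAP*

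**What the plan says.** **Events.** SAP 3.1 and 9.4.1 take the treatment period as Day 1 to Visit 8 (Week 28). Under 5.1.1, antibiotics for a countable PEx must start no later than "Day of Visit 8 or discontinuation from the study". A subject who permanently stops product does not leave the study: under 4.1.12 "they will be asked to continue in the study for efficacy and safety follow-up with Visits 5 and 8 performed off study product". Section 9.2 places assessments made after stopping in the primary efficacy analysis, and 6.4.1 analyses the mITT population regardless of compliance.

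**Person-time.** The denominator in 4.2.1 is "sum of subject treatment exposure durations in the treatment group (days) / 196". Section 8.2.1 defines exposure as last dose minus first dose plus 1, and the Poisson model in 9.4.1 uses the log of the same quantity.

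**Time to first PEx (9.5.3).** A subject with a PEx is timed to the start of antibiotics, with no cut at last dose. A subject without one is censored at last dose.

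**Text pointing the other way.** Section 5.1 says "The occurrence of a new PEx will be assessed throughout the active dosing period". Section 13 calls the analyses generally on-treatment, but then ends the period early only when a subject discontinues the study, not the product.

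**The concern.** A rate is interpretable only if events and time at risk come from the same window. Here, someone who stops product at Week 10 and stays to Week 28 contributes 28 weeks of possible events and 10 weeks of denominator. In the Cox model the same person's end date depends on the outcome: the PEx date if one follows, Week 10 if none does. That is informative censoring created by the rule itself.

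The primary endpoint and secondary endpoints 1 to 7 all rest on these definitions, and 9.3 makes every secondary test depend on the primary. If stopping product differs by arm, the rate ratio and hazard ratio move against the arm that stops more. Two analysts following different sections could also obtain different primary results. Under Section 2 the SAP supersedes the protocol's methods and is not changed after signature except for analyses requested by FDA, so the choice cannot be left open.

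**Working it through.** **The SAP's own figure.** Section 6.3 gives 80% power for a rate ratio of 0.65, placebo rate 0.80, 166 per arm, "accounting for an approximate 15% dropout rate". With 166 × 0.85 = 141 per arm, a Wald test on the log rate ratio gives power = Φ(|ln 0.65| / √(1/(141 × 0.80) + 1/(141 × 0.52)) − 1.96) = Φ(2.872 − 1.96) = 0.82. The figure reproduces. It sets the scale but does not test the mismatch.

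**Formula.** Let F be mean time in the study and E mean time to last dose, with 28 weeks = 1. With log exposure as an offset and no covariates, the SAP ratio divided by the follow-up-time ratio is (Ep/Fp) / (El/Fl), for placebo p and lenabasum l. This holds whatever the event rate after stopping.

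**Assumptions (not in the SAP).**
- 15% of each arm leave the study at uniform times: F = 1 − 0.15 × 0.5 = 0.925.
- A further share d stop product but stay to Week 28. Stops are uniform over 28 weeks (E = 0.925 − 0.5d) or, as an extreme case, uniform within the first 8 weeks (E = 0.925 − (6/7)d).
- For the Cox column only: constant rate, unchanged after stopping.

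| Stopping, 20 mg vs placebo | Calculation (uniform) | Rate-ratio factor: uniform (early) | SAP Cox HR when true HR is 1.00: uniform (early) |
|---|---|---|---|
| equal | – | 1.00 | not tabulated |
| 5% vs 2.5% | 0.9125/0.900 | 1.014 (1.024) | 1.009 (1.015) |
| 10% vs 5% | 0.900/0.875 | 1.029 (1.051) | 1.017 (1.030) |
| 20% vs 5% | 0.900/0.825 | 1.091 (1.171) | 1.057 (1.105) |
| 2.5% vs 5% | 0.900/0.9125 | 0.986 (0.976) | not tabulated |
| 5% vs 10% | 0.875/0.900 | 0.972 (0.951) | not tabulated |

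The Cox values are simulated and good to a few units in the third decimal.

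**Reported rates.** When stopping is equal and the true placebo rate is 0.80, 5% stopping gives 0.80 × 0.925/0.900 = 0.82 (early 0.84), and 10% gives 0.80 × 0.925/0.875 = 0.85 (early 0.88).

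**Effect on the test.** Separate simulations used 166 per arm, full follow-up, uniform stops and an unchanged rate off product. At 15% vs 5% stopping:
- A true ratio of 1.00 becomes 0.975/0.925 = 1.054, and two-sided rejection is 7.7%.
- A true ratio of 0.65 becomes 0.685, and power falls from 88% to 79%.
- With the imbalance reversed, 0.65 becomes 0.617.

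With matched windows the null ratio stays at 1.00 and rejection at about 5%.

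**Separating the error from dilution.** Suppose the rate returns to the placebo level after stopping and the on-product ratio is 0.65. At 10% vs 5%, uniform stops, the follow-up ratio is (0.65 × 0.875 + 0.05)/0.925 = 0.669 and the SAP ratio is 0.669 × 1.029 = 0.688. The step from 0.669 to 0.688 is the error. The step from 0.650 to 0.669 is dilution, which belongs to a follow-up estimand.

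**End date for subjects who leave.** Three dates could apply to a subject lost to follow-up: last scheduled visit attended (9.2), last contact as imputed last dose (8.2.1) and study discontinuation (5.1.1). The event cut-off must match the time cut-off. With 4-weekly visits and leaving uniform over 28 weeks, mean time to leaving is 14 weeks and mean time to the last visit is 12. Stopping the clock at the last visit but counting later events turns 0.80 into 0.80 × 14/12 = 0.93 in leavers. Dropping the later events returns 0.80.

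**The case against.** **The plan leans on-treatment.** The exposure denominator, the active-dosing wording in 5.1, last-dose censoring and Section 13 all point that way. If the PEx rate does not change off product, an on-treatment analysis with events cut at last dose recovers the true ratio equally well, so the choice of window could be left to the sponsor. What stands is that either matched window removes the error. But 5.1.1, 9.2 and 6.4.1 are explicit rules that keep off-product events in the primary analysis, so the follow-up window needs less to be overturned.

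**The shift may be small.** At 5% vs 2.5% and 10% vs 5% it is 1.4% and 2.9%, roughly 0.1 and 0.2 standard errors at 166 per arm. If lenabasum stops more, the excess null rejections fall mostly on the harm side. This stands as a limit on size. With the imbalance reversed (5% vs 10%), however, one-sided false benefit rises from 2.5% to about 4%.

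**Off-product ascertainment is thinner.** Only Visits 5 and 8 are scheduled after stopping. Missed PEx would bias a follow-up rate downward in the arm that stops more. The risk is real but limited: 4.1.3 covers all subjects with new symptoms, who "should contact the site staff and return for a Possible PEx Visit if instructed to do so".

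**The unadjusted rate.** Section 4.2.1 also defines a rate per subject without exposure adjustment, which avoids this denominator. It is descriptive and does not replace the primary model.

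**Conclusion.** The defect is in the text and does not depend on any assumed rate: either events and person-time come from different windows, or the SAP contradicts itself on which events count. No section settles it. Section 4.1.12 promises that "The impact of having these subjects remain in the study will be assessed in sensitivity analyses", but the visible list in 9.4.2 has only per-protocol and negative binomial models with the same exposure term.

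Size and direction cannot be known from the SAP. For modest imbalances in stopping the rate ratio moves by about 1% to 3% (up to 5% if stops come early). At 20% vs 5% it moves by 9% (17% if early). Hazard ratios move by roughly 1% to 6% (up to about 10% if early). With equal stopping the rate ratio is about unbiased and only the absolute rates are overstated. These figures assume no covariates, no overdispersion and an offset. Because this is the primary endpoint and the gate for all secondary tests, it must be fixed before unblinding.

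**What to change.** Define one end date per subject and use it for events, person-time and censoring:

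- Consistent with 5.1.1 and 9.2, end the window at the earlier of Visit 8 and study discontinuation. For withdrawn consent or loss to follow-up, use the last-scheduled-visit rule in 9.2.
- Set the date in the same way whether or not a PEx occurred, count no event after it, and align 5.1.1 with it.
- Use this time in the 4.2.1 denominator. In 9.4.1 state that its log enters as an offset with coefficient 1. The section now lists log exposure among the effects; the rate definitions in 5.1 and 6.2 imply an offset, so one clarifying word is enough.
- In 9.5.3 censor event-free subjects at the same date.
- Reconcile the active-dosing wording in 5.1 and the on-treatment wording in Section 13 with 9.2.
- Unless removed text already specifies it, make the sensitivity analysis promised in 4.1.12 a matched on-treatment analysis, with events and time both cut at last dose, and say that it answers a different question.

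**Cost.** SAP wording and one derived date per subject; no new data. The main rate becomes a rate per time in study and carries any dilution from off-product time. It also relies on PEx being captured after product is stopped. PEx between the last scheduled visit and leaving are not counted for subjects who withdraw consent or are lost.

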4.2.2. Secondary Efficacy Endpoints

The secondary efficacy endpoints include the following, all assessed at or through Visit 8 (treatment phase), as relevant:

- Event rate of new PEx per subject per 28 weeks using secondary definition of new PEx, comparing lenabasum 20 mg BID and placebo cohorts
- Time to first new PEx using primary definition of new PEx, comparing lenabasum 20 mg BID and placebo cohorts
- Time to first new PEx using secondary definition of new PEx, comparing lenabasum 20 mg BID and placebo cohorts
- Event rate of new PEx per subject per 28 weeks, using the primary definition of new PEx, comparing lenabasum 5 mg BID and placebo cohorts.
- Event rate of new PEx per subject per 28 weeks, using secondary definition of new PEx, comparing lenabasum 5 mg BID and placebo cohorts
- Time to first new PEx using primary definition of new PEx, comparing lenabasum 5 mg BID and placebo cohorts
- Time to first new PEx using secondary definition of new PEx, comparing lenabasum 5 mg BID and placebo cohorts
- Change in CFQ-R respiratory symptom domain score for adolescents and adults, comparing lenabasum 20 mg BID and placebo cohorts
- Change in FEV1 % predicted, comparing lenabasum 20 mg BID and placebo cohorts
- Change in CFQ-R respiratory symptom domain score for adolescents and adults, comparing lenabasum 5 mg BID and placebo cohorts
- Change in FEV1 % predicted, comparing lenabasum 5 mg BID and placebo cohorts

[figure not shown]

-
-
-

4.3. Study Safety Endpoints

4.3.1. Primary Safety Endpoints

- TEAEs by treatment cohorts and combined lenabasum cohorts

4.6. Data Monitoring Committee

Oversight of subject safety in this trial will be provided by a DMC subcommittee of the Cystic Fibrosis Foundation Therapeutics Data Safety Monitoring Board and will be an independent group of CF experts that will advise Corbus. The members of the DMC will serve in an individual capacity and provide their expertise and recommendations. The members of the DMC will be recommended to Corbus by the Cystic Fibrosis Foundation Therapeutics Data Safety Monitoring Board Operations Center at the University of Arizona and the European Cystic Fibrosis Society Clinical Trials Network and will include members from both the United States and Europe. Besides CF experts, a member who is experienced in the monitoring of central nervous system AEs will be included in the DMC.

The primary responsibilities of the DMC will be to: 1) periodically review and evaluate the accumulated study data for participant safety, study conduct and progress, and, when appropriate, efficacy; and 2) make recommendations to Corbus concerning the continuation, modification, or termination of the trial.

The DMC will be responsible for defining its deliberative processes, including event triggers that would call for an unscheduled review, stopping guidelines, unblinding and voting procedures before initiating any data review. The DMC is responsible for maintaining the confidentiality of its internal discussions and activities as well as the contents of reports provided to it.

During the trial, the DMC will review cumulative study data to evaluate safety, study conduct, and scientific validity and integrity of the trial and will review efficacy data for a futility analysis. The DMC is expected to review all reported AEs in an unblinded manner. The DMC is

also expected to review confirmatory PK data from a subset of approximately 20 adolescents to estimate the exposure in comparison to about 20 adults. This should yield approximately 8 adolescents receiving lenabasum 20 mg BID and 4 adolescents receiving lenabasum 5 mg BID (8 adolescents receiving placebo). The DMC will have unblinded access to the available PK data and all safety data during this review which will include, at the minimum, Visit 1 post-dose PK data from the subjects under review. The Sponsor, investigative sites and regulatory agencies will remain blinded to the treatment assignments for these DMC reviews and analyses. If indicated by the data, the DMC may recommend changes to dosing in adolescents.

The individual DMC members must be satisfied that the timeliness, completeness, and accuracy of the data submitted to them for review are sufficient for evaluation of the safety and welfare of study participants and futility analysis. Items reviewed by the DMC will be outlined in the DMC Charter and may include:

- Interim/cumulative data for evidence of study-related AEs
- An interim unblinded review of PK data for the first 20 adult and 20 adolescent subjects including available safety data
- Data quality, completeness, and timeliness
- Performance of individual sites
- Adequacy of compliance with goals for recruitment and retention, including those related to the participation of women and minorities
- Adherence to the protocol
- Factors that might affect the study outcome or compromise the confidentiality of the trial data
- Factors external to the study such as scientific or therapeutic developments that may affect participant safety or the ethics of the study
- Interim data for futility analyses.

If there are any unanticipated safety problems during the study, the sponsor's designee will submit available information related to the unanticipated problem to the DMC chair for review. The DMC chair will determine if the unanticipated problem warrants calling an unscheduled full DMC meeting or not. In the case that an unanticipated problem requires a full DMC meeting, the DMC will make a recommendation to the Sponsor regarding suggested corrective actions.

The DMC should conclude each review with their recommendations to Corbus as to whether the study should continue without change, be modified, or terminated.

